## **10 EFFECTIVENESS AND SAFETY VARIABLES**

### **10.1 Effectiveness and Safety Measurements Assessed**

#### **10.1.1 Effectiveness Variables**

##### **10.1.1.1 Intraocular Pressure**

Every attempt should be made to schedule the visits at approximately the same time of day to avoid the influence of diurnal fluctuations on study procedures, specifically measurement of IOP.

Except at the Operative Visit (Visit 2), IOP will be measured at all study visits by standard Goldmann applanation tonometry. The readings will be recorded on the appropriate eCRF. The tonometer should be checked for proper calibration monthly and the date of calibration checking should be recorded. The eye cannot have received pupil-dilating medications.

##### **10.1.1.2 Topical IOP-lowering Medication**

For endpoints evaluating the number of topical IOP-lowering medications taken by the subject, the following are examples of the classes of medications to be recorded: prostaglandin analogues, beta-adrenergic antagonists, CAIs, alpha-adrenergic agonists, pilocarpine, and combinations of these treatments.

##### **10.1.1.3 Patient-reported Outcomes**

The following 3 questionnaires will be completed to assess subject status. Questionnaires will be administered to subjects on an electronic tablet at the visits designated in [Table 8.1](#). Data from completed questionnaires will be imported into the eCRF using a validated process.

1. Collaborative Initial Glaucoma Treatment Study (CIGTS) Symptom and Health Problem Checklist (SHPC-18)
2. Postsurgical question on resumption of activities and daily routine
3. Work Productivity and Activity Impairment (WPAI): Productivity outcomes.

The SHPC-18 is an 18-item questionnaire that asks subjects being treated for glaucoma questions about eye symptoms or problems they may experience. The questionnaire includes 2 domains: local eye symptoms (7 items) and visual function problems (11 items). The development of the SHPC-18 and validation of its 2 domains have been published. Each question first asks the subject if they have experienced the symptom or problem in the last 7 days. If the subject responds “Yes”, they are then asked how

burdensome the symptom or problem was, with Likert-type response options ranging from “Not at all” to “A lot” (Musch et al. 2017).

The WPAI is included because overall work productivity is significantly related to general health perceptions and the global measures of interference with regular activity (Reilly et al. 1993).

Additionally, responses to the Postsurgical Question will be collected to better understand differences, if any, in postoperative recovery between the 2 procedures.

These measures can be found in [Appendix 17](#).

### **10.1.2 Safety Analysis**

Safety analysis will be performed in both the XEN population and the population randomized to trabeculectomy. The numbers and percentage of subjects reporting AEs will be tabulated regardless of causality. AEs, ADEs, and all safety measures will be summarized by frequencies at each visit.

#### **10.1.2.1 Adverse Events**

Throughout the course of the study, all AEs will be monitored and reported on an AE eCRF, including seriousness, severity, action taken, and relationship to study treatment. If AEs occur, the first concern will be the safety of the study participants. Needling and laser suture lysis will be captured as procedures but will not be considered AEs.

All AEs and device deficiencies that occur between visits are to be recorded on the date of the next postoperative examination on the subject’s eCRF.

##### **10.1.2.1.1 Definitions**

The investigators will classify the AEs based on the following definitions according to ISO 14155 (2011).

##### **Adverse Event**

An AE is defined in accordance with ISO 14155 as any untoward medical occurrence, unintended disease or injury, or untoward clinical signs (including abnormal laboratory findings) in subjects, users or other persons, if related to the investigational medical device. This definition includes events related to the investigational medical device or comparator and events related to the procedures involved. Disease signs and symptoms that existed prior to the study treatment are not considered AEs unless the condition recurs after the participant has recovered from the pre-existing condition or the condition worsens in intensity or frequency during the study.

AEs will be monitored throughout the study beginning with the Preoperative Visit. At each postbaseline visit, the investigator will begin querying for AEs by asking each participant a general, nondirected question such as “Have you had any changes to your condition since your last visit?” Previous AEs and changes in therapy/concomitant medications are to be updated. Directed questioning and examination will then be done as appropriate. All reportable AEs and clinically significant abnormal laboratory findings will be documented on the appropriate eCRF.

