#### **10.1.2.1.2 Possible Adverse Events**

The following is a list of AEs that can occur intraoperatively during implantation of XEN and/or trabeculectomy surgery. These and any other AEs that occur should be reported in the AE eCRF:

- Detached Descemet’s membrane
- Iris damage
- Lens contact
- Vitreous bulge or loss
- Anterior chamber bleeding
- Retrobulbar hemorrhage
- Conjunctival perforation

- Conjunctival or scleral flap tearing
- Shallow anterior chamber with peripheral iridocorneal touch
- Flat anterior chamber with iridocorneal touch extending to the pupil
- Device malfunction identified prior to implantation
- Choroidal hemorrhage or effusion

The following is a list of AEs that can occur postoperatively for XEN and/or trabeculectomy surgery. These and any other AEs that occur should be reported in the AE eCRF:

- Angle recession
  - Anterior chamber shallow with peripheral iridocorneal touch
  - Anterior chamber flat with iridocorneal touch
  - BCVA loss of  $\geq 2$  lines ( $\geq 10$  Early Treatment Diabetic Retinopathy Study [ETDRS] letters)
    - $\leq 30$  days
    - $>30$  days
    - At 12 months (persistent loss)
  - Bleb leak (without operative room or slit lamp revision)
  - Bleb leak (with operative room or slit lamp revision)
  - Blebitis (with or without anterior chamber reaction or hypopyon)
  - Cataract formation
  - Clinically significant progression of cataract, based on an assessment by the investigator
  - Choroidal effusion (extending posterior to equator, without blood)
  - Choroidal effusion (obscuring disc or macula, without blood)
  - Choroidal effusion (with choroids touching in the center of the eye, without blood)
  - Choroidal effusion (extending posterior to equator, with blood)
  - Choroidal effusion (obscuring disc or macula, with blood)
  - Choroidal effusion (with choroids touching in the center of the eye, with blood)
  - Choroidal effusion and/or hemorrhage occurring  $>30$  days (persistent)
  - Chronic pain (present greater than 3 months)
  - Corneal edema grade 3 or grade 4 ( $>30$  days postoperatively)
  - Cyclodialysis
  - Dellen
  - Device malfunction
  - Endophthalmitis
  - Fixed dilated pupil
  - Hyphema ( $\geq 2$  mm in height [layered] at any time)
  - Hyphema (present or arising  $>30$  days)
  - Hypotony (IOP  $<6$  mm Hg at any time)
-

- Persistent hypotony (IOP <6 mm Hg at 2 visits >30 days apart)
- Hypotony maculopathy
- Implant exposure
- Implant fracture
- Implant migration

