### **Assessment of Causality**

Relationship to a device refers to a determination of the relationship (if any) between an AE and the device. A causal relationship is present if the investigator determines that there is a reasonable possibility that the AE may have been caused by the device.

An AE could be considered procedure-related when, in the judgment of the investigator, it is reasonable to believe that the event is associated with the procedure, regardless of the relationship to the study device. Procedure-related causes that contribute to the occurrence of the event can be attributed to other products, surgical techniques, or medications required specifically for the procedure.

Every effort will be made by the investigator to assess the relationship of the AE, if any, to the device and/or study procedure. Causality should be assessed using the categories presented in the following table:

- Not related: Clinical event of which the relationship to the device and/or procedure can be excluded, such as if the event is incompatible time relationship to study procedure and/or use of the device, involves a body part or organ not expected to be affected by the device or procedure, could be explained by underlying disease or other drugs or chemicals or is incontrovertibly not related to the study device, and is not due to use error.
- Unlikely: Clinical event whose time relationship to use of the device and/or study procedure makes a causal connection improbable, but that could plausibly be explained by underlying disease or other drugs or chemicals.
- Possible: Clinical event with a reasonable time relationship to the use of the device and/or study procedure, but that could also be explained by concurrent disease or other drugs or chemicals. Cases in which relatedness cannot be assessed or no information has been obtained should also be classified as possible.

Probable:	Clinical event with a reasonable time relationship to the use of the device and/or study procedure, and is unlikely to be attributed to concurrent disease or other drugs or chemicals.

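### The adverse event definition requires relatedness to device, comparator or procedure, which contradicts the plan to record and tabulate events whatever their cause

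*Protocol*

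**What the plan says.** Protocol 10.1.2.1.1 tells investigators to classify events by the definitions that follow it. Under Adverse Event, the condition is that the occurrence is "in subjects, users or other persons, if related to the investigational medical device". The sentence after it reads: "This definition includes events related to the investigational medical device or comparator and events related to the procedures involved". Later in the same text, what goes on the form is described this way: "All reportable AEs and clinically significant abnormal laboratory findings will be documented on the appropriate eCRF". The protocol does not define what makes an AE reportable.

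Elsewhere the protocol is broader:

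- Section 10.1.2: "The numbers and percentage of subjects reporting AEs will be tabulated regardless of causality".
- Section 10.1.2.1: "all AEs will be monitored and reported on an AE eCRF, including seriousness, severity, action taken, and relationship to study treatment".
- Section 10.1.2.1.2, on the listed events: "These and any other AEs that occur should be reported in the AE eCRF".
- Assessment of Causality: the lowest category is a "Clinical event of which the relationship to the device and/or procedure can be excluded".

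Protocol 11.1.4 and SAP 5.6.2 summarise all treatment-emergent AEs and, separately, the treatment-related ones. Under Reporting of Serious Adverse Events (Protocol 10.1.2.1.3), one sentence requires 24-hour data entry for serious events related to the device or surgery. A later sentence in the same text requires every serious event from consent to the final visit to be reported to the sponsor.

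**The concern.** Relatedness should be an attribute scored once an event is on the form. Here it is written as a test for whether the event counts as an AE at all. A site that applies the definition as written could leave out an event it considers unrelated, and no analysis can tabulate what was never entered.

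This matters because comparing safety is half of the study's only objective. The trial is open-label, the investigator judges causality, the protocol has no data safety monitoring board (10.2), and monitoring is remote with visits only when needed (12.2). Any filter before recording would therefore be applied by someone who knows the assigned surgery. At stake are the completeness of the all-cause AE tables and, if sites or arms applied the filter differently, their comparability.

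**Working it through.** This is a question of wording, so no arithmetic applies and the plan has no figure to reproduce. The check sets the definition against each section that depends on it.

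1. **What the definition covers.** The first sentence covers events related to the device. The second adds events related to the comparator or the procedures. An event judged unrelated to all three is left out.

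2. **Tabulation (Protocol 10.1.2).** Counting AEs whatever their cause adds something only if events of every cause are in the database. Under step 1, events with no link to device, comparator or procedure need not be.

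3. **Recording (Protocol 10.1.2.1).** Relationship is listed beside seriousness and severity as something noted for every AE. That treats it as an attribute, whereas the definition treats it as an entry test.

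4. **Causality scale.** The scale has a category for events whose link to device and/or procedure can be excluded. Device and procedure relationships are separate judgements, so the category keeps a use under the literal definition: a procedure-only event can be scored unrelated to the device. It has no use for an event unrelated to both, unless such events are recorded.

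5. **Summaries (Protocol 11.1.4, SAP 5.6.2).** Treatment-related events are shown as a subset of all treatment-emergent events, and nonocular events have their own summary. Both imply that unrelated events are expected.

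6. **Timing.** The definition text itself starts AE monitoring at the Preoperative Visit, before any surgery. That fits poorly with a test of relatedness to device or surgery.

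7. **Serious events.** One sentence limits the 24-hour entry duty to related events. The later one covers all serious events, and adds 24-hour notification on top of data entry. Section 10.1.2.1.3 also defines a serious event as a kind of AE, so the broader sentence inherits the restricted term.

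8. **Which events are exposed.** The lists in Protocol 10.1.2.1.2 name most of the ocular events of interest as AEs. The AE terms used to identify clinical hypotony for the primary endpoint (SAP 5.3.1) all appear there. IOP, visual acuity, visual field and pachymetry are scheduled measurements. What remains is mainly non-serious, unlisted events judged unrelated.

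**The case against.** The strongest reply is that capture is secured elsewhere. All AEs go on the form, listed and any other AEs are to be reported, every participant is asked a general undirected question, and all serious events from consent are reportable. A relationship that cannot be assessed is classed as possible, so doubt favours inclusion. The revision history (Protocol 17.4) explains the any-other-AEs sentence as meaning that all AEs are wanted. This stands as a limit on the likely loss. It does not remove the contradiction, because these sentences use the term AE that the definition restricts, and nothing says that they override it.

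A second reply is that the relatedness clause may govern only users or other persons. Counting a worsened pre-existing condition without a relatedness test fits that reading. But subjects are in the same list, and the next sentence again describes coverage by relatedness. With about 25 to 40 sites, two possible readings are reason enough to clarify.

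A reader might infer three stronger things that the documents do not support:

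- That trabeculectomy events are excluded. The second sentence of the definition covers comparator and procedure events.
- That the unrelated category can never be used. It can, for procedure-only events.
- That the arm comparison is biased by some stated amount. No section supports any rate of omission or a loss confined to one arm. If unrelated events were under-recorded equally, that arm-specific distortion would not arise.

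**Conclusion.** The contradiction is real and rests on the documents' own text, without recourse to the cited ISO standard. The definition excludes events judged unrelated to device, comparator and procedure, while the recording, causality and tabulation text assumes that they are present. Applied literally, it would leave the all-cause AE tables incomplete.

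The exposure is limited, mainly to non-serious, unlisted events judged unrelated. Differential capture by arm is a risk that the open-label design permits; it is not a demonstrated effect. No magnitude can be derived, because the documents do not say how sites applied the definition or what share of events would be judged unrelated. The point does not by itself undermine the primary analysis. It should still be corrected, because the correction is cheap and omitted events cannot be recovered at the analysis stage.

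**What to change.** - In the AE definition, make any untoward occurrence in a subject an AE, whether or not it is related to the device, the comparator or the procedure. Keep the relatedness condition only for users or other persons, and for ADEs and SADEs. Swapping one phrase in the present sentence is not enough: it would make unrelated illness in users or bystanders an AE and leave the next sentence's relatedness wording in place.
- Delete or define the word reportable in the same text.
- Align the two serious-event sentences in Protocol 10.1.2.1.3.
- Tell sites that causality is scored after the event has been recorded.
- If data were already collected under this wording, state in the study report whether unrelated events were captured consistently across sites and arms.

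The cost is a protocol clarification, a site memo and slightly more AE records.

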#### **Adverse Device Effect (ADE)**

An ADE is defined in accordance with ISO 14155 as “an adverse event related to the use of an investigational medical device.” This definition includes any AEs resulting from insufficient or inadequate instructions for use, deployment, implantation, installation, or operation, or any malfunction of the investigational medical device as well as any event resulting from use error (per ISO 62366) or from intentional misuse of the investigational medical device.

#### **Device Deficiency or Complaints**

A device deficiency is defined in accordance with ISO 14155 as inadequacy of a medical device including issues with respect to its identity, quality, durability, reliability, safety or performance. Device deficiencies include malfunctions, use errors, and inadequate labeling.

If a device deficiency occurs, the investigator will notify Allergan using the eCRF. Device deficiencies shall be documented throughout the study and appropriately managed by Allergan. The Clinical Trial Site will enter all the information regarding device deficiency into the appropriate eCRFs. Allergan shall review all device deficiencies and determine and document in writing whether they could have led to the SADE. These shall be reported to the regulatory authorities and independent ethics committees/institutional review boards (IECs/IRBs) as required by Federal regulations.

#### **10.1.2.1.2 Possible Adverse Events**

The following is a list of AEs that can occur intraoperatively during implantation of XEN and/or trabeculectomy surgery. These and any other AEs that occur should be reported in the AE eCRF:

- Detached Descemet’s membrane
- Iris damage
- Lens contact
- Vitreous bulge or loss
- Anterior chamber bleeding
- Retrobulbar hemorrhage
- Conjunctival perforation

- Conjunctival or scleral flap tearing
- Shallow anterior chamber with peripheral iridocorneal touch
- Flat anterior chamber with iridocorneal touch extending to the pupil
- Device malfunction identified prior to implantation
- Choroidal hemorrhage or effusion

The following is a list of AEs that can occur postoperatively for XEN and/or trabeculectomy surgery. These and any other AEs that occur should be reported in the AE eCRF:

- Angle recession
  - Anterior chamber shallow with peripheral iridocorneal touch
  - Anterior chamber flat with iridocorneal touch
  - BCVA loss of  $\geq 2$  lines ( $\geq 10$  Early Treatment Diabetic Retinopathy Study [ETDRS] letters)
    - $\leq 30$  days
    - $>30$  days
    - At 12 months (persistent loss)
  - Bleb leak (without operative room or slit lamp revision)
  - Bleb leak (with operative room or slit lamp revision)
  - Blebitis (with or without anterior chamber reaction or hypopyon)
  - Cataract formation
  - Clinically significant progression of cataract, based on an assessment by the investigator
  - Choroidal effusion (extending posterior to equator, without blood)
  - Choroidal effusion (obscuring disc or macula, without blood)
  - Choroidal effusion (with choroids touching in the center of the eye, without blood)
  - Choroidal effusion (extending posterior to equator, with blood)
  - Choroidal effusion (obscuring disc or macula, with blood)
  - Choroidal effusion (with choroids touching in the center of the eye, with blood)
  - Choroidal effusion and/or hemorrhage occurring  $>30$  days (persistent)
  - Chronic pain (present greater than 3 months)
  - Corneal edema grade 3 or grade 4 ( $>30$  days postoperatively)
  - Cyclodialysis
  - Dellen
  - Device malfunction
  - Endophthalmitis
  - Fixed dilated pupil
  - Hyphema ( $\geq 2$  mm in height [layered] at any time)
  - Hyphema (present or arising  $>30$  days)
  - Hypotony (IOP  $<6$  mm Hg at any time)
-

- Persistent hypotony (IOP <6 mm Hg at 2 visits >30 days apart)
- Hypotony maculopathy
- Implant exposure
- Implant fracture
- Implant migration
- Implant obstruction (complete or partial)
- Implant repositioning requiring surgical intervention
- Increase in cup/disc ratio of  $\geq 0.3$  units on slit lamp examination
- Increase in corneal thickness of  $\geq 10\%$  in the presence of corneal edema
- IOP increase  $\geq 10$  mm Hg from baseline
- Iridodialysis
- Iritis (requiring treatment after the postoperative medication taper)
- Loss of eye
- Macular edema
- Macular puckering
- Posterior capsule opacification
- Ptosis
- Retinal complications
- Secondary surgical intervention
  - Explant
  - Secondary glaucoma procedure with explant
  - Secondary glaucoma procedure
- Significant (2-grade) worsening or a grade of moderate or severe, for any slit lamp observation for which a standard grading scale is not available (>30 days postoperatively)
  - Anterior chamber cells
  - Blepharitis
  - Chalazion
  - Dysesthetic bleb
  - Hyperemia
- Significant iris injury or atrophy
- Strabismus
- Suture abscess or other local infection
- Vitreous hemorrhage
- Vitreous loss
- Wound leak/dehiscence

### **Assessment of Severity**

Severity is a clinical determination of the intensity of an AE. The severity assessment for a clinical AE will be assigned a category by the investigator as follows:

- Mild: An AE that is easily tolerated by the subject, causes minimal discomfort, may require only minimal treatment and does not interfere with everyday activities.
- Moderate: An AE that is sufficiently discomforting to interfere with normal everyday activities; intervention may be needed, but poses no significant or permanent risk of harm.
- Severe: An AE that prevents normal everyday activities; treatment or other intervention usually needed.

If there is a change in severity of an AE, it must be recorded as a separate event.

### **Assessment of Causality**

Relationship to a device refers to a determination of the relationship (if any) between an AE and the device. A causal relationship is present if the investigator determines that there is a reasonable possibility that the AE may have been caused by the device.

An AE could be considered procedure-related when, in the judgment of the investigator, it is reasonable to believe that the event is associated with the procedure, regardless of the relationship to the study device. Procedure-related causes that contribute to the occurrence of the event can be attributed to other products, surgical techniques, or medications required specifically for the procedure.

Every effort will be made by the investigator to assess the relationship of the AE, if any, to the device and/or study procedure. Causality should be assessed using the categories presented in the following table:

- Not related: Clinical event of which the relationship to the device and/or procedure can be excluded, such as if the event is incompatible time relationship to study procedure and/or use of the device, involves a body part or organ not expected to be affected by the device or procedure, could be explained by underlying disease or other drugs or chemicals or is incontrovertibly not related to the study device, and is not due to use error.
- Unlikely: Clinical event whose time relationship to use of the device and/or study procedure makes a causal connection improbable, but that could plausibly be explained by underlying disease or other drugs or chemicals.
- Possible: Clinical event with a reasonable time relationship to the use of the device and/or study procedure, but that could also be explained by concurrent disease or other drugs or chemicals. Cases in which relatedness cannot be assessed or no information has been obtained should also be classified as possible.

Probable:	Clinical event with a reasonable time relationship to the use of the device and/or study procedure, and is unlikely to be attributed to concurrent disease or other drugs or chemicals.
Causal relationship:	Clinical event with plausible time relationship to the use of the device and/or study procedure, is a known side effect of the product category the device belongs to or of similar devices and procedures; follows a known response pattern to the medical device; involves a body-site or organ that the device or procedures are applied to and/or influence; harm is due to error in use, and that cannot be explained by concurrent disease or other drugs or chemicals.

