##### **Reporting of Serious Adverse Events**

All device- or surgery-related SAEs must be entered into the EDC system within 24 hours of being notified of the event. The sponsor will be notified by EDC system once the SAE electronic form has been submitted.

The relationship of the clinical event to the devices and procedure should be reported on the Serious Adverse Event Form for Devices and will be determined by the investigator.

Following evaluation of each SAE, the responsible IEC/IRB will be notified as appropriate based on national regulations.

All SAEs that occur from the time the informed consent form (ICF) is signed through to their final study visit must be reported to the sponsor. In addition to entering the information into the EDC system, the investigator must:

- Notify the sponsor immediately (within 24 hours) by fax using the Serious Adverse Event Form for Devices. The form should be sent directly to the sponsor at [LC-Medical\\[contact]](mailto:[contact]) or fax to [contact] or [contact]. The SAE report should be completed regardless of the amount of information available although the investigator is expected to provide as much information as possible.
- Obtain and maintain in his/her files all pertinent medical records, information, and medical judgments from colleagues who assisted in the treatment and follow-up of the subject.
- Provide the sponsor with a complete, written case history (AE report form) which includes a statement as to whether the event was or was not related to the use of the investigational device or procedure.

The sponsor (or its representative) will report all SAEs associated with the use of the study device to the regulatory agencies (IEC/IRB, Competent Authorities) as appropriate according to relevant SOPs and to the national laws of the country where the trial is performed.

For every SAE, appropriate measures should be taken to treat/resolve and monitor the subject. The investigator should keep Allergan closely informed of the progress as related to the SAE. Any subjects who are withdrawn from the study due to an AE shall still be followed up until the outcome is resolved.

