5.6.2. Adverse Events

Adverse events will be coded by system organ class (SOC) and preferred term (PT) using the Medical Dictionary for Regulatory Activities (MedDRA), version #21.0 or newer.

Adverse events will be classified to either ocular AEs or nonocular AEs. An ocular AE will be determined as indicated on the AE form of eCRF, and thus are not limited to AEs with primary SOC of eyes. The adverse events will be also classified to either AE or adverse device effect (ADE). The summary of AEs will be separately done for nonocular AEs, ocular AEs and ADEs. Ocular AEs and ADEs will be tabulated by treatment group for the study, and nonocular AEs will be summarized by treatment group for participants. eye

An AE will be considered a treatment emergent adverse event (TEAE) if the AE began or worsened (increased in severity or became serious) on or after the date (and time, if known) of the surgery.

An TEAE and ADE will be considered a TESA or SADE if it meets any SAE criterion.

Overall summary of TEAEs will be provided for categories of all TEAEs, treatment-related TEAEs/TEADEs, TESA/TEADE, deaths, TEAEs/TEADEs leading to study discontinuation, TEAEs/TEADEs, treatment-related TEAEs/TEADEs, TESA/TEADEs and TEAEs/TEADEs leading to study discontinuation will be further classified into ocular and nonocular subcategories.

The number and percentage of participants reporting TEAEs/TEADEs in each treatment group will be tabulated by SOC in descending frequency order of XEN first, then by preferred term in descending frequency order of XEN, and further categorized by severity. If more than 1 AE/ADE is coded to the same preferred term for the same participant, the participant will be counted only once for that preferred term using the greatest severity and strictest causality for the summarization by severity and causal relationship.

The number and percentage of participants with treatment-related TEAEs/TEADEs will be tabulated by SOC and preferred term.

Summary tables will be provided for participants with TESA and participants with TEAEs/TEADEs leading to discontinuation. Listings of all AEs, SAEs, and AEs leading to discontinuation by participant will be presented.

The same analysis will be repeated for ocular TEAEs/TEADEs, ocular TESA/TEADEs.

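### One example under the *Not related* causality category contradicts that category's own condition and overlaps *Possible* and *Unlikely*, so treatment-related, ADE and SADE counts are open to inconsistent classification

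*Protocol*

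**What the plan says.** Protocol 10.1.2.1.2, Assessment of Causality, gives the investigator five categories.

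- *Not related* opens with a governing condition, "Clinical event of which the relationship to the device and/or procedure can be excluded, such as if". Examples joined by 'or' follow: incompatible timing, a body part that the device or procedure would not affect, and that the event "could be explained by underlying disease or other drugs or chemicals or is incontrovertibly not related to the study device". The entry closes by also requiring that use error is not the cause.
- *Unlikely* is for an event whose timing "makes a causal connection improbable, but that could plausibly be explained by underlying disease or other drugs or chemicals".
- *Possible* is defined as a "Clinical event with a reasonable time relationship to the use of the device and/or study procedure, but that could also be explained by concurrent disease". It carries a default: "Cases in which relatedness cannot be assessed or no information has been obtained should also be classified as possible".
- *Probable* and *Causal relationship* need another explanation to be unlikely or unavailable.

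The section also states a general rule: device causation is taken to be present where the investigator sees a reasonable possibility of it.

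Several outputs use the category. SAP 5.6.2 says: "The number and percentage of participants with treatment-related TEAEs/TEADEs will be tabulated by SOC and preferred term". It also divides events into AEs and ADEs, and it takes the strictest causality when a participant has repeated events under one preferred term. Protocol 10.1.2.1.1 defines an ADE by its relation to the device, and 10.1.2.1.3 defines a SADE as an ADE with a serious consequence. Both are safety endpoints in Protocol 7.2. Neither document says which of the five categories make an event treatment-related or an ADE. The design is open-label and there is no data safety monitoring board (Protocol 10.2).

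**The concern.** That an event could have another cause does not rule out the device or the procedure. It is the usual reason for choosing a middle category. Offered as an example of a relationship that can be ruled out, it gives the investigator the wrong guidance about what *Not related* means.

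The events exposed are those with plausible timing after surgery and a conceivable disease explanation. The postoperative list in 10.1.2.1.2 contains terms for which an investigator could raise underlying eye disease, such as BCVA loss, cataract progression, an increase in cup/disc ratio and a rise in IOP. Two investigators could place the same event in different categories, each pointing to protocol text. At stake is the consistency of the treatment-related table and of the ADE and SADE counts.

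**Working it through.** No arithmetic applies: the plan states no figure on this point and gives no event rates. The check sets the definitions side by side and runs three kinds of event through them.

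**1. What each category requires**

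| Category | Timing | Alternative explanation | Other condition |
|---|---|---|---|
| Not related | Bad timing is one example, not a requirement | That one could apply is itself an example | Relationship can be ruled out; no use error |
| Unlikely | Makes causation improbable | Could plausibly apply | None |
| Possible | Reasonable | Could also apply | Default for cases that cannot be assessed |
| Probable | Reasonable | Unlikely | None |
| Causal relationship | Plausible | Cannot account for the event | Known pattern, affected site, and further listed features |

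A possible alternative cause appears in three of the five rows. Only in *Not related* is it listed without a timing element attached.

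**2. Three test events**

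- *Reasonable timing, disease could explain it.* This meets the *Possible* definition in full. It also matches the disputed example under *Not related*, but it fails that category's governing condition, because nothing has been ruled out. The example and its own heading give opposite answers.
- *Improbable timing, disease could plausibly explain it.* This meets *Unlikely* and again matches the disputed example. On wording alone, *Unlikely* is the closer match, since both it and *Not related* refer to underlying disease while *Possible* refers to concurrent disease.
- *Cannot be assessed.* The default sends this to *Possible*. There is no conflict.

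**3. Against the general rule.** A well-timed event with one conceivable alternative can still leave a reasonable possibility of device causation. The general rule then finds causation present, while the disputed example permits *Not related*.

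**4. Which outputs move**

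- *Depend on the category:* treatment-related TEAEs (SAP 5.6.2; Protocol 11.1.4), and ADEs and SADEs through their definitions.
- *Do not depend on it:* AE counts tabulated regardless of causality (Protocol 10.1.2), the lists of events of interest (SAP 5.6.2.1), and the primary endpoint (SAP 5.3.1), whose criteria do not include causality.

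**5. A second gap.** Moving an event from *Not related* to *Possible* changes a count only if *Possible* counts as related. Neither document sets that cut-off, so the counts would remain unclear even with clean category definitions.

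**The case against.** The strongest reply is that the governing condition controls. The items after it are illustrations, use error must also be absent, and an investigator who reads the whole entry would not file a well-timed event with a possible device cause as *Not related*. That stands as the better reading of the scale. It does not remove the fault, because examples are there to show how a condition is applied and this one shows it wrongly.

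Five stronger readings are tempting, and the documents do not support them:

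- *That a conceivable alternative cause is enough by itself for Not related, or that the category uses the same words as Possible.* The governing condition still applies, and *Possible* adds reasonable timing and differs in wording.
- *That every doubtful case must default to Possible.* The default covers only cases that cannot be assessed or have no information.
- *That the overlap biases the comparison between arms.* One scale serves both arms. Differential judgement would come from the open label, and it would remain after the clause is corrected.
- *That serious device events would go unreported.* Protocol 10.1.2.1.3 requires all SAEs from consent to the final visit to reach the sponsor within 24 hours, with a statement on relatedness. The sponsor "will report all SAEs associated with the use of the study device to the regulatory agencies", so the category may inform onward reporting, but the sponsor has the event whatever its category.
- *That the effect can be sized.* Multiplying an assumed share of ambiguous events by arm size only returns the assumption. The 68 and 34 eyes in SAP Section 3 are also completers, whereas the safety tables use operated eyes.

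**Conclusion.** The concern holds as an internal contradiction in the causality scale. One example under *Not related* conflicts with that category's condition and with the section's reasonable-possibility rule, and it overlaps *Possible* and *Unlikely*. The consequence is that treatment-related TEAE, ADE and SADE counts are open to inconsistent classification. To call them irreproducible would go further than the text allows.

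The size is unknown and cannot be derived from the documents. The effect on related counts assumes that *Possible* is treated as related, which fits the reasonable-possibility rule but is not stated. The finding that all-causality counts are safe assumes that the tabulation sentence in Protocol 10.1.2 governs; the AE definition in 10.1.2.1.1 has relatedness wording of its own, which is not examined here. The point is worth correcting, but it does not touch the primary analysis.

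**What to change.** In Protocol 10.1.2.1.2, delete the could-be-explained example from *Not related*, or reword it to agree with the governing condition, for example: is shown to be due to another cause. Leave alternative-explanation wording only under *Unlikely* (improbable timing) and *Possible* (reasonable timing).

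As a supporting step, state in SAP 5.6.2 that Possible, Probable and Causal count as treatment-related in both arms, in line with the reasonable-possibility rule, and say which categories make an event an ADE. The SAP sentence alone would not recover events already filed as *Not related*, so the protocol clause needs correcting too.

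The cost is a wording amendment, which needs ethics committee or IRB approval under Protocol 14.1, plus one or two SAP sentences. Related counts may come out slightly higher. Events already classified would need the investigator to re-check the category. No new data field or analysis is needed.
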